#### 7.1.2. Study Dose

In accordance with the Guideline on the Investigation of Bioequivalence (1), a dose of 120 mg has been selected for the study as the IMP shows linear pharmacokinetics with no safety/tolerability concerns at this dose level (2).

#### 7.1.3. Fasting/Fed Conditions

Study drug administration will be performed under fasting conditions as per Guideline on the Investigation of Bioequivalence (1), which states that products for which the SmPC recommends the intake of the Reference medication irrespective of food, bioequivalence studies should be carried out in the fasted state as it is considered the most sensitive condition to detect a potential difference between formulations.

#### 7.1.4. Choice of Volunteers

Only healthy volunteers will be enrolled in this study in accordance with the Guideline on the Investigation of Bioequivalence (1), which states that healthy subjects are regarded as an adequate population to reduce variability not related to differences between products and also allow extrapolation of the results to populations for which the reference medicinal product is approved (the elderly, children, patients with renal or liver impairment, etc.).

The study eligibility criteria have been chosen to only allow participation of males.

As the present study is intended for European registration, where the representative race of the general adult population is Caucasian, only Caucasian subjects will be enrolled in this study.

According to the EMA Guideline (1), subjects should be at least 18 years old to participate in the study. Elderly subjects (i.e. over 55 years of age) will not be eligible for this study as they are likely to have a high incidence of AEs due to higher plasma levels of etoricoxib when compared to adults (2).

In accordance with the EMA Guideline (1), subjects should preferably have a BMI between 18.5 and 30 kg/m^2 to participate in the study. These BMI limits are commonly used as an enrolment criteria for studies in healthy volunteers and are therefore considered adequate for this study.

#### 7.1.5. Choice of Analyte

The assessment of BE will be based on the plasma drug levels of etoricoxib parent drug in this study. This approach is in line with the EMA Guideline on Bioequivalence studies and it is based on the rationale that the parent drug is the most sensitive analyte to detect differences in the concentration-time profile between the study formulations (1).

#### 7.1.6. Pk Sampling Schedule

The study pk sampling schedule has been planned to ensure frequent sampling around predicted  $t_{max}$  of etoricoxib following a single oral administration. Samples will be collected up to 72 hours post-dose to provide a reliable estimate of the extent of exposure to etoricoxib (2). Further details on pk sampling schedule are provided in [Section 14.1](#).

### 7.1.7. Washout Period

Based on the  $t_{1/2}$  of etoricoxib (22 hours) (2), a washout period of at least 14 days has been selected to ensure the IMP is completely eliminated from the body between study periods.

Washout period will occur between Day 1 Period 1 and Day 1 Period 2. Subjects will remain in confinement at the CU during the washout period and repeated forehead body temperature measurements will be taken.

### 7.1.8. COVID-19 RT-PCR Tests

Due to COVID-19's (Coronavirus disease – 19) pandemic safety measures, subjects will be confined during four nights in a hotel near the CU ([name]).

Tests will be performed on Day -5, Day -2 of screening and the day before subject's discharge from the CU as part of the FU visit. Repeated forehead body temperature measurements will be taken throughout the confinement.

In case of positive result for any COVID-19 RT-PCR test, it will be notified to Turkish Ministry of Health for further safety actions out of the study's scope.

## 7.2. Measures to Minimise Bias

The following measures to reduce bias will be implemented:

- Subjects will be sequentially assigned to receive either Test or Reference product in a random fashion.
- Eligibility of subjects will be based on the fulfilment of all study inclusion and exclusion criteria.
- The CU staff will monitor and record subject's compliance and any non-compliance with the protocol requirements.

The Bioanalytical Laboratory staff will not have access to the study randomisation list.

## 8. ELIGIBILITY OF SUBJECTS

The below eligibility criteria have been set for the study:

## 8.1. Inclusion Criteria

Volunteers must meet all of the following criteria to be eligible for enrolment in the study:

1. Caucasian males.
2. Subjects aged between 18 and 55 years (inclusively) at the date of signing Informed Consent Form (ICF) which is defined as the beginning of the screening period.
3. Subjects must have a BMI at screening within 18.5 to 30.0 kg/m^2, inclusively.
4. Willingness to adhere to the protocol requirements and to provide written, personally signed, and dated ICF to participate in the study before the start of any study-related procedures.
5. Availability for the entire duration of the study.

6. Motivated subjects with absence of intellectual problems likely to limit the validity of consent to participate in the study or the compliance with protocol requirements; ability to cooperate adequately; ability to understand and observe the instructions of the physician or designee.
7. Satisfactory medical assessment at screening with no clinically relevant abnormalities as determined by medical history, physical examination, ECG, and clinical laboratory evaluation (haematology, biochemistry and urinalysis) that are reasonably likely to interfere with the subject's participation in or ability to complete the study as assessed by the Investigator.
8. Subjects must agree to abstain from xanthine-containing products (i.e. coffee, tea, cola, energy drinks, chocolate, etc.) from 48 hours prior to the first study drug administration until the end of confinement.
9. Subjects must agree to abstain from poppy seed-containing products from 48 hours prior to the first study drug administration until the end of confinement.
10. Subjects must agree to abstain from alcohol from 48 hours prior to the first study drug administration until the end of study.
11. Subjects must not consume and agree to continue to abstain from St John's Wort, vitamins and herbal remedies from 2 weeks prior to the first study drug administration until the end of confinement.
12. Subjects must not consume and agree to continue to abstain from beverages or food containing orange, grapefruit or pomelo from 2 weeks prior to the first study drug administration until the end of confinement.
13. Subjects must agree to use medically acceptable methods of contraception during the study and for 30 days after the end of the study. Medically acceptable methods of contraception include using a condom with a female partner of childbearing potential who is using oral contraceptives, hormonal patch, implant or injection, intrauterine device, or diaphragm with spermicide. Complete abstinence alone can be used as a method of contraception.

## 8.2. Exclusion Criteria

Subjects will be excluded from enrolment in the study if they meet any of the following criteria:

1. History of significant hypersensitivity to etoricoxib or any related products (including excipients of the formulations) as well as severe hypersensitivity reactions (such as angioedema) to any drug.
2. Presence of significant gastrointestinal, liver or kidney disease, or any other conditions known to interfere with the absorption, distribution, metabolism or excretion of drugs or known to potentiate or predispose to undesired effects.
3. History of major surgery of the gastrointestinal tract except for appendectomy.
4. History of significant gastrointestinal, liver or kidney disease that may affect the drug BA.
5. Presence of significant cardiovascular, respiratory, genitourinary, musculoskeletal, hematologic, neurological, psychiatric, endocrine, immunologic or dermatologic disease.
6. Presence of respiratory infection symptoms (COVID-19 infection symptoms) like fever, dry cough, nasal congestion or sore throat.

7. Having COVID-19 infection or having been in contact to people with known COVID-19 infection in the last 14 days.
8. Use of tobacco in any form (e.g., smoking or chewing) or other nicotine-containing products in any form (e.g., gum, patch, electronic cigarettes) within 6 months prior to Day 1 Period 1.
9. History of controlled or uncontrolled hypertension or clinically relevant systolic blood pressure (SBP), diastolic blood pressure (DBP) and/or heart rate (HR) readings outside the normal ranges at screening (Day -3) or prior to drug administration on Day 1 Period 1. Normal ranges are the following:
  - SBP: 90 to 140 mmHg
  - DBP: 60 to 90 mmHg
  - HR: 50 to 100 beats/min
10. Forehead body temperature readings outside the range of 35.5 to 37.4°C at screening (Day -5, -4, -3, -2, -1) or prior to the first drug administration.
11. Any planned surgery involving general, spinal or epidural anaesthesia from 3 months prior to Day 1 Period 1 to 7 days after last dosing.
12. Known presence of rare hereditary problems of galactose and/or lactose intolerance, lactase deficiency or glucose-galactose malabsorption.
13. Any clinically significant illness within 30 days prior to Day 1 Period 1.
14. Use of any enzyme-modifying drugs, including strong inhibitors of cytochrome P450 (CYP) enzymes (such as cimetidine, fluoxetine, quinidine, erythromycin, ciprofloxacin, fluconazole, ketoconazole, diltiazem and Human Immunodeficiency Virus (HIV) antivirals) and strong inducers of CYP enzymes (such as barbiturates, carbamazepine, glucocorticoids, phenytoin and rifampicin) within 30 days prior to Day 1 Period 1.
15. Use of Over the Counter (OTC) medications within 7 days prior to Day 1 Period 1. It will be specifically reminded that this includes cold preparations, acetylsalicylic acid (ASA), natural products used for therapeutic benefits and antacid preparations.
16. Intake of any prescription medication within 30 days prior to Day 1 Period 1.
17. Maintenance therapy with any drug or significant history of drug dependency.
18. Alcohol abuse, i.e. regular use of more than 10 units per week (one unit of alcohol equals 250 mL of beer, 125 mL of wine or 25 mL of spirits), a history of alcoholism or recovered alcoholics.
19. Positive alcohol, drugs of abuse or cotinine results at screening (Day -1).
20. Positive result on Day -5 and/or Day -2 of screening on COVID-19 RT-PCR test.
21. History of drug abuse or use of illegal drugs: use of soft drugs (e.g. marihuana) within 6 months of screening or hard drugs (e.g. amphetamines, barbiturates, benzodiazepines, cannabinoids, cocaine and opioids) within 1 year of screening.
22. A positive Human Immunodeficiency Virus antibody (HIV-Ab) screen, Hepatitis B surface antigen (HBsAg) or Hepatitis C Virus (HCV) tests.
23. Use of an investigational product within 60 days prior to Day 1 Period 1 or active enrolment in another drug or vaccine clinical study.

24. Use of depot injectable solutions with a half-life of >1 week within 6 months prior to Day 1 Period 1.
25. Subjects previously randomised in this study.
26. An inability to follow a standardised diet and meal schedule or inability to fast, as required during the study.
27. Donation of blood (at least 100 mL) or plasma by plasmapheresis within 30 days prior to Day 1 Period 1.
28. Volunteers who report difficulty swallowing tablets as a whole.

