**5.2.3. Pharmacodynamic Properties**

Its pharmacotherapeutic group is anti-inflammatory and antirheumatic products, non-steroids, coxibs.

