#### **5.2.5. Contraindications, Interactions, Overdose and Special Warnings for Use**

##### *Contraindications*

- Hypersensitivity to the active substance or to any of the excipients in the Arcoxia formulation.
- Active peptic ulceration or active gastro-intestinal (GI) bleeding.
- Patients who, after taking acetylsalicylic acid or NSAIDs including COX-2 (cyclooxygenase-2) inhibitors, experience bronchospasm, acute rhinitis, nasal polyps, angioneurotic oedema, urticaria, or allergic-type reactions.
- Pregnancy and lactation.
- Severe hepatic dysfunction (serum albumin <25 g/l or Child-Pugh score ≥10).
- Estimated renal creatinine clearance <30 ml/min.
- Children and adolescents under 16 years of age.
- Inflammatory bowel disease.
- Congestive heart failure (NYHA II-IV).
- Patients with hypertension whose blood pressure is persistently elevated above 140/90 mmHg and has not been adequately controlled.
- Established ischaemic heart disease, peripheral arterial disease, and/or cerebrovascular disease.

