### Fluid retention, oedema and hypertension

As with other medicinal products known to inhibit prostaglandin synthesis, fluid retention, oedema and hypertension have been observed in patients taking etoricoxib. All Nonsteroidal Anti-inflammatory Drugs (NSAIDs), including etoricoxib, can be associated with new onset or recurrent congestive heart failure. Caution should be exercised in patients with a history of cardiac failure, left ventricular dysfunction, or hypertension and in patients with pre-existing oedema from any other reason. If there is clinical evidence of deterioration in the condition of these patients, appropriate measures including discontinuation of etoricoxib should be taken.

Etoricoxib may be associated with more frequent and severe hypertension than some other NSAIDs and selective COX-2 inhibitors, particularly at high doses. Therefore, hypertension should be controlled before treatment with etoricoxib and special attention should be paid to blood pressure monitoring during treatment with etoricoxib. Blood pressure should be monitored within two weeks after initiation of treatment and periodically thereafter. If blood pressure rises significantly, alternative treatment should be considered.

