#### General

If during treatment, patients deteriorate in any of the organ system functions described above, appropriate measures should be taken and discontinuation of etoricoxib therapy should be considered. Medically appropriate supervision should be maintained when using etoricoxib in the elderly and in patients with renal, hepatic, or cardiac dysfunction.

Caution should be used when initiating treatment with etoricoxib in patients with dehydration. It is advisable to rehydrate patients prior to starting therapy with etoricoxib.

Serious skin reactions, some of them fatal, including exfoliative dermatitis, Stevens-Johnson syndrome, and toxic epidermal necrolysis, have been reported very rarely in association with the use of NSAIDs and some selective COX-2 inhibitors during post-marketing surveillance. Patients appear to be at highest risk for these reactions early in the course of therapy with the onset of the reaction occurring in the majority of cases within the first month of treatment. Serious hypersensitivity reactions (such as anaphylaxis and angioedema) have been reported in patients receiving etoricoxib. Some selective COX-2 inhibitors have been associated with an increased risk of skin reactions in patients with a history of any drug allergy. Etoricoxib should be discontinued at the first appearance of skin rash, mucosal lesions, or any other sign of hypersensitivity.

Etoricoxib may mask fever and other signs of inflammation.

Caution should be exercised when co-administering etoricoxib with warfarin or other oral anticoagulants.

The use of etoricoxib, as with any medicinal product known to inhibit cyclooxygenase / prostaglandin synthesis, is not recommended in women attempting to conceive.

Arcoxia tablets contain lactose. Patients with rare hereditary problems of galactose intolerance, the Lapp lactase deficiency or glucose-galactose malabsorption should not take this medicine.

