### 11.2.2. Medical and Surgical History

Personal, family allergy and/or disease history will be recorded as well as surgical history.

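### Exclusion 1 is narrower than the protocol's own contraindications, so a volunteer with a past non-severe reaction to aspirin or an NSAID is not clearly excluded

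*Protocol*

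**What the plan says.** Exclusion 1 in Protocol Section 8.2 bars a volunteer with a "History of significant hypersensitivity to etoricoxib or any related products (including excipients of the formulations) as well as severe hypersensitivity reactions". The severe limb covers reactions to any drug and gives angioedema as its example. The terms 'significant', 'severe' and 'related products' are not defined.

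Section 5.2.5, under Contraindications, summarises the reference product's label. Two entries matter here. One is hypersensitivity to the active substance or an excipient, with no qualifier. The other reads "Patients who, after taking acetylsalicylic acid or NSAIDs including COX-2 (cyclooxygenase-2) inhibitors, experience bronchospasm, acute rhinitis, nasal polyps, angioneurotic oedema, urticaria" and closes with allergic-type reactions in general, also with no qualifier.

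Section 9 lists precautions against adverse events. It says that people who have had a hypersensitivity reaction to etoricoxib or related products, excipients included, cannot enrol. The word 'significant' does not appear there.

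The history needed to apply any of these rules is collected at screening. Section 11.2.2 states: "Personal, family allergy and/or disease history will be recorded as well as surgical history".

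**The concern.** The rule that decides who is dosed is looser than the contraindication printed in the same protocol. A volunteer can fit the contraindication and still pass Exclusion 1, depending on how three undefined terms are read.

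The participants are healthy, and Section 9 accepts that they gain no medical benefit beyond a health examination. Each takes 120 mg twice. Section 5.2.5 (General) reports serious hypersensitivity reactions with etoricoxib and adds: "Some selective COX-2 inhibitors have been associated with an increased risk of skin reactions in patients with a history of any drug allergy". That warning carries no severity threshold either, although it is a caution about some drugs in the class and not a contraindication.

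What is at stake is subject safety only. The comparison of the two products is not affected.

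**Working it through.** No arithmetic decides this point, so the check sets the texts side by side.

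**1. Which text governs.** Section 7.2, repeated in SAP Section 7, rests eligibility on the inclusion and exclusion criteria. Section 11.2 has staff check the case report forms against Section 8, and Section 11.3.1 re-evaluates the same criteria at admission. Section 5.2.5 is background; nothing turns its contraindications into an eligibility rule.

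**2. Thresholds compared.**

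| Past history | Section 5.2.5 | Exclusion 1 | Section 9 |
|---|---|---|---|
| Non-severe reaction to etoricoxib or an excipient | Contraindicated | Excluded only if 'significant' | Ineligible |
| Severe reaction to ASA or an NSAID | Contraindicated | Excluded | Ineligible if the drug is a 'related product' |
| Non-severe reaction to ASA or an NSAID | Contraindicated | Excluded only if the drug is 'related' and the reaction 'significant' | Ineligible if the drug is a 'related product' |

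In the first row the protocol contradicts itself, but Section 9 is clear. The gap lies in the third row.

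**3. Does 'related products' include NSAIDs?** The protocol gives grounds for saying so. Section 5.2.3 states: "Its pharmacotherapeutic group is anti-inflammatory and antirheumatic products, non-steroids, coxibs". Section 5.2.5 speaks of "All Nonsteroidal Anti-inflammatory Drugs (NSAIDs), including etoricoxib". This is an inference, however, because no section defines the term. For ASA it takes a further step, since the contraindication names ASA alongside NSAIDs.

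**4. A worked case.** A volunteer once had mild urticaria after ibuprofen. He meets the contraindication. The first limb of Exclusion 1 catches him only if ibuprofen is a related product and mild urticaria is significant. The second limb does not catch him unless the reaction is called severe.

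**5. Other routes to exclusion.**
- Exclusion 2 is mandatory in form and covers the presence of conditions "known to potentiate or predispose to undesired effects". Sections 5.2.5 (Contraindications) and 5.2.5 (General) give a documented basis for applying it, but whether a past drug reaction is a present condition is a matter of reading.
- Inclusion 7 concerns clinically relevant abnormalities "that are reasonably likely to interfere with the subject's participation in or ability to complete the study as assessed by the Investigator". A mild reaction years ago need not interfere with either.
- Exclusion 5 requires significant disease at present.
- Section 8.3 lets the principal investigator withdraw a subject in that subject's best interest, which is discretionary.
- Exclusion 15 is the only criterion that mentions ASA, and it concerns use in the preceding 7 days, not past reactions.

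None of these names a reaction to ASA or an NSAID.

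**6. Size.** The ASA/NSAID contraindication lists 6 reaction types with no severity qualifier. Exclusion 1 names 1 of them (angioedema), leaving 6 − 1 = 5 unnamed. This counts wording, not exposure: a severe reaction of any of the 5 types is excluded, and a non-severe one may be, by judgement. The documents give no prevalence, so the count cannot be turned into a number of volunteers.

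**The case against.** The best reply combines Section 9 with Exclusion 2. If 'related products' includes NSAIDs, as the protocol's own classification suggests, Section 9 makes any volunteer with a past NSAID hypersensitivity reaction ineligible, however mild. Exclusion 2 says such people will be excluded if they have a condition known to predispose to undesired effects; the test is not the investigator's opinion, and drug hypersensitivity can reasonably be seen as a continuing predisposition. Allergy history is recorded, eligibility is re-evaluated at admission, and discontinuation criteria are checked before dosing. A careful physician would see the history and knows the contraindication.

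Most of this stands, and it shrinks the point. It does not remove it. Section 9 helps only through an undefined term, and staff are told to check Section 8, where the qualifier remains. Exclusion 2 needs an interpretation that two investigators could make differently.

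A reader might infer that the plan allows contraindicated volunteers to be dosed, or that 5 of the 6 reaction types go unexcluded. The documents support neither. Severe reactions to any drug are barred, and several routes can stop a volunteer with a milder history. The text shows only that his exclusion is not clearly required.

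**Conclusion.** The point holds as a minor, inexpensive improvement. Exclusion 1 is narrower than the contraindications in Section 5.2.5 and inconsistent with Section 9. The remaining gap is a past, non-severe reaction to ASA or an NSAID that nobody judges significant.

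The conclusion assumes that Section 8 is the operative rule, as Sections 7.2, 11.2 and 11.3.1 indicate, and that the undefined terms are left to site judgement. If the sponsor has a written definition of related products that includes ASA and all NSAIDs, Section 9 already covers the case and only the inconsistency with Exclusion 1 is left.

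The consequences are limited by supervision: Section 11.3.3 keeps the investigator on site for at least 4 hours after dosing, and Section 13.1 provides emergency equipment. A reader might also infer some threat to the trial's result. There is none: sample size, power, analysis population and acceptance limits do not depend on this criterion.

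**What to change.** Reword Exclusion 1 along these lines:

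*Any past hypersensitivity to etoricoxib or to an excipient of either product; any past urticaria, angioedema, bronchospasm, acute rhinitis, nasal polyps or other allergic-type reaction following an NSAID (COX-2 inhibitors included) or acetylsalicylic acid; or a severe hypersensitivity reaction to any other drug.*

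This drops 'significant', removes the undefined 'related products', and keeps the severe threshold for unrelated drugs. Use the same wording in Section 9.

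No new procedure is needed, since allergy history is already taken at screening. The cost is a protocol amendment under Section 17, a matching line in the eligibility check of the case report form, and possibly a few more screen failures, in a number the documents do not allow one to estimate.
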